#### 12.5. Reporting Adverse Events to ICR-CTSU

Any toxicity, sign or symptom that occurs after commencement of study treatment and within 30 days of the last administration of study treatment, which is not unequivocally due to progression of disease, should be considered an AE. All AEs must be reported on the relevant toxicity, sign or symptom eCRF.

The severity of AEs should be graded according to CTCAE v4 and RTOG criteria. For each toxicity/sign/symptom, the highest grade observed since the last visit should be reported.

Whenever one or more toxicity/sign/symptom corresponds to a disease or a well-defined syndrome only the main disease/syndrome should be reported.

#### 12.6. Reporting Serious Adverse Events to ICR-CTSU

Any SAE (except those in section 12.7) that occurs after the commencement of study treatment (including fiducial marker/HDR implant) and up to 30 days following the last administration of study treatment must be reported and RTOG grade  $\geq 3$  acute or late radiation side effects occurring within 5 years after radiotherapy treatment should be reported to ICR-CTSU as described below.

All SAEs should be reported to ICR-CTSU within 24 hours of the Principal Investigator (or designated representative) becoming aware of the event by completing the PIVOTALboost SAE form. The completed SAE form should be sent by email to [[contact]](mailto:[contact])

As much information as possible, including the Principal Investigator's assessment of causality, must be reported to ICR-CTSU in the first instance. Additional follow up information should be reported as soon as it is available.

All SAE forms must be completed signed and dated by the Principal Investigator or designated representative.

The Site SAE log should be completed and the SAE form filed in the Site Investigator File.

### **12.7. Expected Adverse Events**

The following adverse events are considered expected if grade  $\leq 3$  and are exempt from expedited reporting to ICR-CTSU but should be reported using the appropriate CRF.

- Haematuria
- Dysuria/frequency
- Nausea/vomiting
- Prostate spasms or pain
- Diarrhoea
- Abdominal pain
- Urinary tract infection
- Urinary/clot retention
- Erectile Dysfunction ( $\leq$ grade 3)

### **12.8. Review of Serious Adverse Events**

The Chief Investigator (or designated representative) will assess all reported SAEs for causality and expectedness (NB. The Chief Investigator cannot down-grade the Principal Investigator's assessment of causality.)

SAEs assessed as having a causal relationship to study treatment and as being unexpected will undergo expedited reporting to the relevant authorities and all other interested parties by ICR-CTSU (see section 13.7).

Sites should respond as soon as possible to requests from the Chief Investigator or designated representative (via ICR-CTSU) for further information that may be required for final assessment of an SAE.

### **12.9. Expedited Reporting of Related Unexpected SAEs**

If an SAE is identified as being related and unexpected by the Chief Investigator it will be reported by ICR-CTSU to the main REC, the Sponsor and all other interested parties within 15 days of ICR-CTSU being notified of the event.

The Principal Investigators at all actively recruiting sites will be informed of any related unexpected SAEs occurring within the trial at regular intervals.

**12.10. Follow up of Serious Adverse Events**

SAEs should be followed up until clinical recovery is complete or until the condition has stabilised. SAE outcomes should be reported to ICR-CTSU using the relevant section of the SAE form as soon as the Principal Investigator becomes aware of the outcome.

[figure not shown]
**12.11. Annual reporting of safety considerations**

An annual progress report will be provided to the main REC by ICR-CTSU and copied to the Sponsor, if applicable, the collaborative group in each participating country at the end of the reporting year. This will include data about related unexpected SAEs and whether any safety concerns have arisen during the reporting period.

**12.12. Reporting pregnancies**

If any trial participants' partner becomes pregnant whilst the trial participant is receiving trial treatment or up to 90 days after receiving trial treatment, this should be reported to ICR-CTSU using the pregnancy reporting form. Pregnancies should be followed up until conclusion and all follow-up information should be reported to ICR-CTSU. If the outcome of the pregnancy meets the definition of serious (i.e. congenital abnormality) this should be reported to ICR-CTSU following the serious adverse event reporting procedures described above.

Figure 2: Flow diagram for SAE reporting and action following report

NB. All SAEs should continue to be followed up as specified above

## 13. STATISTICAL CONSIDERATIONS

### 13.1. Statistical design and sample size

It is assumed that Failure Free Survival (FFS) at 5 years in the control arm (A) will be 80%. This estimate is based on unpublished data from high risk patients in CHHiP, which showed 5-year biochemical progression free rates of 84.4% [2]. Results from the M0 control cohort of the STAMPEDE trial [64] (a higher risk group than planned for PIVOTALboost), i.e. a FFS of 75% at 5 years in a subgroup of M0 N0 patients with planned RT (n=121) have also been considered.

#### Initial sample size calculation:

The study was powered to detect a 7% difference in 5-year FFS for each experimental arm compared to A (B, C or D) from 80% to 87%. This difference corresponds to a hazard ratio (HR) of 0.624 for each experimental arm as compared to A. This HR was chosen as sufficient to warrant a change in practice in the knowledge that more extreme effects have been reported in similar settings e.g. HR=0.47 in the ASCENDE trial [65]. In order to adjust for multiplicity [66] the 2-sided significance level for each comparison is set to 0.017 (0.05/3). As it was acknowledged that it could be easier to recruit more patients in the A vs. B comparison (see section 13.2 below), we allowed for more patients in the A vs. B comparison:

- to achieve 85% power to detect a 7% difference in 5 year FFS between A and B, 517 patients per group are needed (502 per group to observe 217 events, plus 3% for loss to follow-up).
- to achieve 80% power to detect a 7% difference in 5 year FFS between A and C (or A vs. D), a total of 918 patients are needed (a total of 892 to observe 193 events, plus 3% for loss to follow-up). The overall sample size for A vs C (A vs D) remains the same when the allocation ratio A:C (A:D) is 2:3 or 1:1.

Treatment allocation will be by minimisation. For the 2 way randomisation (A vs B) the ratio will be 1:1. Treatment allocation in the 4 arm randomisation was based on using a 2:2:3:3 ratio initially as it was expected fewer sites will be able to offer boost treatment groups (C and D). The plan was to closely monitor recruitment and adjust the allocation ratio in the 4 arm randomisation to 1:1:1:1 to ensure 9:9:8:8 (517:517:459:459) final relative numbers. The overall sample size was therefore **1952** patients.

#### Updated sample size calculation:

Recruitment to the 4 arm randomisation was slower than expected and the switch to 1:1:1:1 was not made. This has meant that the sharing of arm A patients for the B comparisons compared to the C and D comparisons is less than expected (from assumed 90% (459:517) it is around 20% (144 shared A's out of 763) by February 2022). This means that recruitment into A vs C vs D needs to continue beyond arm B completing target recruitment.

The sample size for A vs C and A vs D has been revisited under this scenario, keeping the same sample size assumptions, but allowing for the fact that recruitment would not be complete in 4.5 years. With the recruitment period extended by 2 years to 6.5 years and the pattern of staggered recruitment to date used the following is true:

- to achieve 80% power to detect a HR of 0.624 (translating to a 7% difference in 5 year FFS between A and C (or A vs. D), assuming 5 year event free rate of 80% in arm) and retaining a conservative alpha of 0.017, 192 events are required (under 1:1 allocation). This number of events would be observed if 847 patients, (822 plus 3% for loss to follow-up) are recruited over 6.5 years and followed up for 5 years. The overall sample size for A vs C (A vs D) remains the same when the allocation ratio A:C (A:D) is 2:3 or 1:1.

Once arm B has completed target recruitment, the trial will recruit patients to arms A, C and D in the ratio 1:1:1. Recruitment will be complete when 847 patients have been randomised to Arms A and C and 847 patients have been randomised to Arms A and D. Overall, the total recruitment across all four arms will be 2195 (see appendix 4, for details based on recruitment up to Feb 2022).

The sample size calculation is based on the log-rank test using the 'artsurv' command in STATA, incorporating 4.5 years of staggered recruitment and a minimum of 5 years of follow-up.

### **13.2. Treatment Allocation**

During the design of the study, it was acknowledged that recruitment and allocation into the different treatment arms could evolve during the trial, given the number of sites open, and the type of boost available at each site. We ran simulations to explore how this would affect time to complete overall recruitment. Following this, we decided to start the trial using an allocation ratio of 2:2:3:3, so it favours the boost groups C or D in a period where it is expected less sites would be offering the boost treatment groups. The allocation ratio may be adjusted during the trial to ensure 9:9:8:8 final relative numbers. Recruitment will be closely monitored and allocation ratios will be monitored annually. On completing recruitment to AvB comparison, the treatment allocation will be 1:1:1 A:C:D.

Full details on the allocation ratio and simulation study will be provided in the Statistical analysis Plan.

Treatment allocation is by minimisation with a random element; balancing factors will be:

- Randomisation Option 1: centre, NCCN risk group (intermediate, high) and suitable volume for focal boost (yes/no).
- Randomisation Option 2a/2b: centre, NCCN risk group (intermediate, high), suitable boost volume for focal boost (yes/no), type of boost (whole gland HDR, focal HDR or focal IMRT) – the last 2 factors will be combined to obtain excluding categories.

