#### Box 1. Suitable focal boost volume

In summary, a **suitable focal boost** volume is defined as:

On the **pre-biopsy** staging multiparametric MRI (mpMRI) scan, a dominant intra-prostatic lesion (DIL) has:

- A score 4 or 5 lesion (clinical significant cancer is likely or highly likely to be present) according to the (PI-RADS (v.2) guidelines. Both T2 and DWI are important and this depends on tumour location in the gland.
- DIL >5mm axial dimension – minimum (>10mm if patient is NCCN intermediate risk).
- Total DIL volume estimated to be <50% total prostate volume. If there are 2 or 3 DILs, add the individual volumes. Volumes can be estimated with measurement of dimension in 3 directions.

Patients with **post-biopsy MRI** won't be eligible for a focal boost, but can receive a whole gland boost if suitable for HDR.

Patients will be assessed weekly during RT, then at 6, 8, 12, 18 weeks; 6, 12, 18 and 24 months, then annually up to 10 years from the start of RT. RT side effects and patient reported outcomes will be assessed up to 5 years. Longer-term follow-up will include PSA levels (routine testing) and details of disease recurrence and deaths.

For certain time period/s during the COVID19 pandemic recruitment may be suspended, restricted or focussed to certain (otherwise eligible) patient groups (e.g. to those geographically close to treatment centres). Details of these changes to the eligible population will be circulated to all open centres and included in the Trial Master File.

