### **13.6. Analysis plan**

The principal analysis will occur after a median follow-up of five years or the target numbers of events have been reached, whichever occurs first. A total of 820 events (217 events x 2 (A, B) + 193 events x 2 (C, D)) to detect a difference of 7% with 85% (A vs B) or 80% (A vs C, D) power is required. Should the analysis not be event driven, the timing will be subject to approval from the IDMC.

The primary comparisons will compare each of the experimental arms to the standard (i.e. A vs B, A vs C and A vs D) and will include all randomised patients (intention-to-treat analysis). Only contemporaneously randomised controls will be used for the A vs C and A vs D comparisons. As secondary analyses, comparisons between experimental arms will also be reported, as well as the overall impact of prostate IMRT vs prostate and pelvis IMRT (A+C vs B+D) and no prostate boost vs prostate boost (A+B vs C+D). Exploratory analysis of the heterogeneity of treatment effect across whole gland or focal boosts, and type of focal boost (IMRT or HDR) will be performed.

All treatment effects will be presented with 2-sided 95% confidence intervals. Adjustment will be made for multiple testing as appropriate. Time to event endpoints will be summarised presenting estimated Kaplan-Meier curves (by treatment); the time point of primary interest is 5 years from randomisation, which will be presented with 95% CI for each treatment arm. Treatment effects will be estimated and tested for significance by the Cox proportional hazards model, adjusting by stratification factors.

Adjusted models will include the duration of ADT prior to starting radiotherapy (as a result of COVID19 related delays to radiotherapy starting). Further models adjusting by other important known prognostic factors will also be fitted. Methods to account for non-proportionality will be used if appropriate. Acute and late side effects will be summarised as frequencies and percentages at each time point. Acute toxicity will also be summarised as worst toxicity reported during radiotherapy. The proportion experiencing grade $\geq$ 2 side effects will be presented; comparisons between treatment groups will be tested using chi-squared or Fishers exact tests. Logistic regression models will be used to estimate treatment differences (odds ratios). Analysis of QL and health economic endpoints are further detailed in Section 20.

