#### A4. Sample size details for updated sample size

##### Overall sample size and extra number of patients needed.

Initial sample size			
Initial recruitment A vs B:	1034		
Initial recruitment C and D:	918		
Total initial overall recruitment:	1952		
Updated sample size (6.5 years recruitment)			
A vs C (A vs D):	847		
Estimated numbers recruited based on Feb 2022 recruitment: (A vs B numbers 994 at this date, estimates assumes B completed recruitment)			
Treatment Allocation	Randomisation option		Total
	1	2	
A	373	144	517
B	371	146	517
C		212	212
D		212	212
Total	724	674	1458
Numbers needed to complete: A vs C and A vs D			
Current no A vs C	356		
remainder A vs C	491	(847-356=491)	
remainder A	246		
remainder C	246		
remainder D	246		
Total sample size:			
Total A+C+D	1306	(=144+ 2x212 +3x246)	
A's in A+C+D already counted in AvB	-144*		
Total A+B	1034		
Total overall (A+B+C+D)	2196		
Additional numbers needed:	244	(=2196-1952)	

\*These A's are those from the 4-way randomisation option and are included in the A vs B numbers.

Recruitment numbers used in the sample size calculation with 6.5 years of recruitment are based on the numbers recruited to date and then 100 patients recruited to A, C per 6 months (and a further 50 to D).

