**Stata code for sample size:**

```
artsurv, method(l) nperiod(23) ngroups(2) fp(0) edf0(0.8, 10) hratio(1, 0.624) ///  
alpha(0.017) power(0.8) aratios(1 1 ) recrt(13 0, 0.034 0.051 0.059 0.048 0.027 0.038  
0.044 0.089 0.122 0.122 0.122 0.122 0.122 , 0 ) ///  
distant(0) detail(0) onesided(0) ni(0) tunit(2) trend(0)
```

Note: the Stata code uses 1:1 ratio, however the actual ratio at the end will be somewhere between 2:3 (the ratio used for the 4-arm randomisation) and 1:1 (the ratio used for the 3-arm randomisation). Using 1:1 and 2:3 results in a different number of events required but the same number of patients to reach that number of events so has no impact on the actual sample size, therefore 1:1 has been used for simplicity.

This protocol is a controlled document and should not be copied, distributed or reproduced without the written permission of the ICR-CTSU

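### The A:C and A:D allocation ratio changes from 2:3 to 1:1 part-way through, but the stated primary Cox model has no term for allocation period, which leaves the boost hazard ratios open to confounding by any prognostic drift

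*Protocol*

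**What the plan says.** Section 13.1 (initial calculation) gives the early ratio: "Treatment allocation in the 4 arm randomisation was based on using a 2:2:3:3 ratio initially". A later move to equal allocation was planned, but the updated calculation reports: "Recruitment to the 4 arm randomisation was slower than expected and the switch to 1:1:1:1 was not made". The 2:3 ratio of A to C, and of A to D, therefore held until arm B completed. Section 13.2 sets what follows: "On completing recruitment to AvB comparison, the treatment allocation will be 1:1:1 A:C:D".

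Appendix 4 builds the boost-comparison total as "144+ 2x212 +3x246": 144 early A, 212 early C and 212 early D, then 246 more in each arm. Its closing note accepts that "the actual ratio at the end will be somewhere between 2:3 (the ratio used for the 4-arm randomisation) and 1:1", but treats this only as a sample-size matter.

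Section 13.2 lists the balancing factors for Options 2a/2b as centre, NCCN risk group, and boost volume combined with boost type. Section 13.6 says: "Treatment effects will be estimated and tested for significance by the Cox proportional hazards model, adjusting by stratification factors". It adds that adjusted models will include the duration of ADT before radiotherapy, and that A vs C and A vs D will use only controls randomised contemporaneously.

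**The concern.** When the allocation ratio changes during a trial, the arms are comparable by randomisation within each ratio period, but not across the pooled set. Arms C and D hold proportionally more early-period men than arm A. If early and late men differ in baseline failure hazard, an analysis that ignores period attributes part of that difference to the boost.

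The contemporaneous-controls rule protects against a different problem, arm A men recruited when C or D was not open. Here both periods contain concurrent A, C and D men, so the rule removes nobody and the imbalance remains.

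A vs C and A vs D are two of the three primary comparisons. They share arm A and have the same early/late imbalance, so drift would push both in the same direction.

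**Working it through.** **Inputs.** Early A 144, C 212, D 212 and late 246 each (Appendix 4). HR 0.624, two-sided alpha 0.017, 80% power, 192 events, 822 patients plus 3% giving 847, 6.5 years of accrual plus 5 years of follow-up, control 5-year FFS 80% (section 13.1). Accrual weights are from the Stata code in Appendix 4. The size of any drift is my assumption.

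**The plan's own figure.** The control hazard is −ln(0.80)/5 = 0.0446 per year. With the Appendix 4 weights and a data cut at 11.5 years, the mean event probability over the two arms is 0.2335. Then 192/0.2335 = 822, and 822 × 1.03 = 847. The Schoenfeld formula gives 188 events and the Freedman formula 195, on either side of the stated 192. The plan's figures reproduce.

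**Early-period share.**
- Arm A: 144/(144 + 246) = 144/390 = 36.9%.
- Arm C or D: 212/(212 + 246) = 212/458 = 46.3%.
- Gap: 9.4 percentage points. The A + C total is 848, which matches 847 up to rounding.

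**Hand check of the bias.** Let r be the late/early hazard, with no treatment effect. The ratio of average hazards, C to A, is [(212 + 246r)/458] / [(144 + 246r)/390].
- r = 0.7: 0.8389/0.8108 = 1.035.
- r = 1: 1.000.
- r = 1.43: 1.2310/1.2712 = 0.968.

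**Cox estimate.** I solved the large-sample score equation of a Cox model without covariates, with exponential survival, the Appendix 4 accrual pattern, the 11.5-year cut and early-period control FFS of 80% at 5 years. The standard error of the log HR is 1/√[events × (390/848) × (458/848)]. The critical value for 0.85% per side is 2.387. The chance of a false positive favouring boost is Φ(−2.387 − shift), where shift = ln(HR)/SE.

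| Late/early hazard (assumed) | HR under no effect | Events | Shift in z | False positive favouring boost |
|---|---|---|---|---|
| 0.7 | 1.030 | 208 | +0.22 | 0.5% |
| 0.8 | 1.019 | 219 | +0.14 | 0.6% |
| 1.0 | 1.000 | 240 | 0 | 0.85% |
| 1.25 | 0.981 | 265 | −0.15 | 1.3% |
| 1.43 | 0.970 | 282 | −0.25 | 1.6% |

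If late men do better (r below 1), the bias runs against boost. If late men do worse, it favours boost.

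**Cost of stratifying.** The information is proportional to 144 × 212/356 + 246 × 246/492 = 85.8 + 123.0 = 208.8 with period strata, and to 390 × 458/848 = 210.6 without. The ratio is 0.991. By Schoenfeld the required events are 188 at 1:1 and 189 at 390:458.

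**The case against.** Several points on the other side stand.

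- **Population.** A reader might infer that closing Option 1 changed who is eligible for A vs C and A vs D. It did not. Option 1 men could receive only A or B (section 10.1), and Appendix 4 counts in the boost comparisons only the 144 early A men, noting: "These A's are those from the 4-way randomisation option and are included in the A vs B numbers". The 373 Option 1 men in arm A were never part of these comparisons.
- **COVID timing.** The extended-ADT allowance dates from about March 2020, inside the 2:3 period. A change within a period of constant ratio does not by itself cause this bias. It matters only if the average mix of men differs between the two ratio periods. Section 3 does say that "recruitment may be suspended, restricted or focussed to certain (otherwise eligible) patient groups" during the pandemic, but its one example is geographic and has no stated link to prognosis.
- **Adjustment already planned.** Centre and NCCN risk group are in the model, and pre-radiotherapy ADT duration is in adjusted models. These would absorb some drift. The figures above come from a model without covariates and so are on the high side for the drift assumed. None of these covariates identifies period, however, and ADT duration is only a partial proxy.
- **The SAP.** It is not shown. Section 13.2 defers allocation-ratio details to it, and it may already contain a period term. But section 13.6 itself names the adjustment set for the primary test, and period is not in it.
- **Size.** A twofold difference between periods has no basis in the document. The two external 5-year rates quoted in section 13.1, 84.4% and 75%, come from different trial populations, and even their hazards differ only by ln(0.75)/ln(0.844) ≈ 1.7.

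**Conclusion.** The concern holds as a vulnerability of the stated model. The ratio change, the 37% versus 46% split and the absence of a period term all follow from the protocol.

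A reader might go further and conclude that the boost hazard ratios are confounded with calendar time. The documents do not support that. Bias needs a difference in baseline hazard across the ratio change, and the protocol neither documents nor quantifies one. With no drift the bias is zero, and its direction is otherwise unknown.

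For an assumed late/early hazard of 0.7 to 1.43, the hazard ratio moves by about 3% at most, which is small beside the target of 0.624. The one-sided error is affected more: at 1.43, the chance of wrongly favouring boost is nearly double its nominal 0.85%. These figures rest on the Appendix 4 projection from February 2022 recruitment, a single step in hazard at the ratio change, exponential survival, and no absorption by covariates.

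**What to change.** In section 13.6, and in the SAP if it does not already say so, stratify the primary A vs C and A vs D Cox models and tests by allocation period (before or after the change to 1:1:1), in addition to adjusting for the balancing factors. Under a two-period model this removes the bias. Kaplan-Meier estimates within period, or standardised over period, are optional.

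The cost is one sentence. Randomisation date and option are already held, so no new data or patients are needed. About 99% of the information is kept, and the 192 events and 847 patients per comparison stand. The stratum should be fixed before any comparative FFS results are seen, so that it is not a post-hoc choice.
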